4.4.2.1 Corticosteroids

Pirfenidone should not be used in combination with high-dose corticosteroids (>15 mg/day) for periods longer than 28 days. Co-administration of pirfenidone with lower doses of corticosteroids is at the discretion of the investigator.

4.4.2.2 Fluvoxamine and Other CYP1A2 Inhibitors

In a Phase I study, the co-administration of pirfenidone and fluvoxamine (a strong inhibitor of CYP1A2 with inhibitory effects on other CYP isoenzymes [CYP2C9, 2C19, and 2D6]) resulted in a 4-fold increase in exposure to pirfenidone in non-smokers ([Esbriet SmPC 2015](#)). Pirfenidone is therefore contraindicated in patients who are receiving concomitant fluvoxamine. Fluvoxamine treatment should be discontinued prior to the initiation of pirfenidone therapy and avoided during therapy due to the reduced clearance of pirfenidone. Other therapies that are inhibitors of both CYP1A2 and one or more other CYP isoenzymes involved in the metabolism of pirfenidone (e.g. CYP2C9, 2C19, and 2D6) should be avoided during pirfenidone treatment.

In vitro and *in vivo* extrapolations have indicated that strong and selective inhibitors of CYP1A2 (e.g. enoxacin) have the potential to increase the exposure to pirfenidone by approximately 2 to 4-fold ([Esbriet SmPC 2015](#)). If concomitant use of pirfenidone with a strong and selective inhibitor of CYP1A2 cannot be avoided, the dose of pirfenidone should be reduced to 801 mg daily (one capsule TID).

Co-administration of pirfenidone and 750 mg of ciprofloxacin (a moderate inhibitor of CYP1A2) increased the exposure to pirfenidone by 81% ([Esbriet SmPC 2015](#)). If ciprofloxacin at a dose of 750 mg BID cannot be avoided, the dose of pirfenidone should be reduced to 1602 mg daily (two capsules TID). Pirfenidone should be used with caution when ciprofloxacin is used at a dose of 250 mg or 500 mg once or twice daily. Pirfenidone should also be used with caution in patients treated with other moderate inhibitors of CYP1A2 (e.g. amiodarone, propafenone).

Caution should be exercised if CYP1A2 inhibitors are being used concomitantly with pirfenidone and potent inhibitors of one or more of the other CYP isoenzymes involved in the metabolism of pirfenidone ([Esbriet SmPC 2015](#)). These isoenzymes include CYP2C9 (inhibitors include amiodarone and fluconazole), CYP2C19 (inhibitors include chloramphenicol), and CYP2D6 (inhibitors include fluoxetine and paroxetine).

4.4.2.3 CYP1A2 Inducers

Concomitant use of strong inducers of CYP1A2 should be avoided during pirfenidone therapy following the results of a Phase I interaction study that found that pirfenidone exposure was 50% lower in smokers compared with non-smokers ([Esbriet SmPC 2015](#)). Smoking induces the CYP1A2 isoenzyme. Patients should therefore be encouraged to discontinue the use of strong inducers of CYP1A2 and to stop smoking before and during treatment with pirfenidone.

In the case of moderate inducers of CYP1A2 (e.g. omeprazole), concomitant use may theoretically result in a lowering of pirfenidone plasma levels ([Esbriet SmPC 2015](#)).

Co-administration of pirfenidone with medicinal products that act as potent inducers of both CYP1A2 and the other CYP isoenzymes involved in the metabolism of pirfenidone (e.g., rifampicin) may result in significant lowering of pirfenidone plasma levels ([Esbriet SmPC 2015](#)). These medicinal products should therefore be avoided whenever possible.

4.4.2.4 Other Medications

The above lists of medications are not necessarily comprehensive. Thus, the investigator should consult the prescribing information for any concomitant medication as well as the Internet references provided below when determining whether a certain medication strongly inhibits or induces CYP1A2. In addition, the investigator should contact the Medical Monitor if questions arise regarding specific medications not listed above.

<http://www.fda.gov/downloads/Drugs/GuidanceComplianceRegulatoryInformation/Guidances/UCM292362.pdf>

<http://medicine.iupui.edu/clinpharm/ddis/table.aspx>

4.4.3 Prohibited Food

The consumption of grapefruit juice will be prohibited from the start of screening through to the Follow-up visit.

4.4.4 Additional Restrictions

The use of any tobacco product will be prohibited from 12 weeks prior to the start of screening through to the Follow-up Visit.

4.5 TRIAL ASSESSMENTS

Please see [Appendix 1](#) for the Schedule of Assessments to be performed during the trial.

4.5.1 Informed Consent Forms and Screening Log

Written informed consent for participation in the trial must be obtained before performing any trial-related procedures. Informed Consent Forms for enrolled patients and for patients who are not subsequently enrolled will be maintained at the trial site.

All screening evaluations must be completed and reviewed to confirm that patients meet all eligibility criteria before enrollment. The investigator will maintain a screening log to record details of all patients screened and to confirm eligibility or record reasons for screening failure, as applicable.

4.5.2 Medical History and Demographic Data

Medical history includes clinically significant respiratory diseases (asthma, chronic obstructive pulmonary disease, and pneumonia), reproductive status, smoking history, use of alcohol, and drugs of abuse. In addition, all medications (e.g., prescription drugs, over-the-counter drugs, vaccines, herbal or homeopathic remedies, nutritional supplements) used by the patient from the washout period until 28 days after the last dose of trial treatment will be recorded.

Demographic data will include age, sex, and self-reported race/ethnicity.

4.5.3 Physical Examinations

A complete physical examination will be performed at screening and will include an evaluation of the head, eyes, ears, nose, and throat, and the cardiovascular, dermatological, musculoskeletal, respiratory, gastrointestinal, genitourinary, and neurological systems. Any abnormality identified at baseline should be recorded on the General Medical History and Baseline Conditions eCRF.

At subsequent visits (or as clinically indicated), limited, symptom-directed physical examinations will be performed (see the Schedule of Assessments; [Appendix 1](#)). Changes from baseline abnormalities should be recorded in patient notes. New or worsened clinically significant abnormalities should be recorded as adverse events on the Adverse Event eCRF.

4.5.4 Vital Signs

Vital signs will include measurements of respiratory rate, pulse rate, and systolic and diastolic blood pressures while the patient is in a seated position, and temperature. All vital sign measurements are to be obtained prior to any blood draws scheduled at the same time.

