5.1.1.7 Weight loss

In the pooled Phase 3 analysis (PIPF-004/006/016), the adverse event of weight decrease was reported for a larger proportion of pirfenidone patients than placebo patients (10.1% pirfenidone vs. 5.4% placebo), and the majority of pirfenidone patients who reported an adverse event of weight decrease first did so during the initial 6 months of treatment (39/63, 61.9%). In the pirfenidone group, two (0.3%) patients had Grade 3 adverse events, one (0.2%) patient had a serious adverse event, and five (0.8%) patients discontinued trial treatment for this adverse event; there were no Grade 4 events, hospitalizations, or deaths. In the placebo group, one (0.2%) patient had a serious adverse event and was hospitalized; there were no Grade 3 or 4 events, deaths, or treatment discontinuations for this adverse event. See Sections 5.4.2.14 and 6.4.1 of the Investigator's Brochure for more details.

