5.1.1.8 Management of Increases in QT Interval

In the event of a QTcF interval of >500 ms or an increase from baseline of >60 ms, a repeat ECG must be obtained within 24 hours. If the QTcF finding is confirmed by the repeat ECG and verified by the site (trial center) or local cardiologist, pirfenidone treatment should be discontinued and a decision on trial treatment discontinuation should be made, as described in Section 4.6.1.. If an alternative explanation is identified (e.g., electrolyte abnormalities, co-medications known to prolong the QT interval, and

severe bradycardia) and the abnormality resolves, restarting trial treatment should be considered by the investigator in consultation with the Medical Monitor or designee. If the investigator, in consultation with the Medical Monitor or designee, considers it clinically appropriate to recommence trial treatment, treatment should be restarted as described in [Table 2](#) .

5.1.2 **Management of Patients Who Experience Specific Adverse Events**

Guidelines for management of specific adverse events are outlined in [Table 3](#) .

Table 3 Guidelines for Management of Patients Who Experience Specific Adverse Events with Pirfenidone

Event	Action to Be Taken
Elevated aminotransferase results	
 • For patients with a >3 to <5 × ULN increase in ALT or AST levels without hyperbilirubinemia: 
 • Discontinue confounding medications • Monitor the patient closely, including repeating liver chemistry tests • Maintain the full daily dose, if clinically appropriate, or reduce or interrupt the dose (e.g., until liver chemistry test results are within normal limits) with subsequent re-titration to full dose if well tolerated. • For patients with a >3 to <5 × ULN increase in ALT or AST levels with symptoms or hyperbilirubinemia: 
 • Discontinue pirfenidone and do not rechallenge the patient. • For patients with a >5 × ULN increase in ALT or AST levels: 
 • Trial treatment should be permanently discontinued.
Gastrointestinal disorders	
 • Dose modifications may be necessary in some cases of gastrointestinal adverse reactions. • Taking pirfenidone with food is recommended.

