- ^c After completion of the double-blind treatment period and the Follow-up Visit at Week 28, the Sponsor will offer the possibility to the patients to receive open-label pirfenidone within the trial protocol in a safety follow-up period of up to 12 months. During the 12-month safety follow-up period, initially, patients will be evaluated at monthly visits for the first 6 months. At the end of the first 6 months, patients will be evaluated at each site visit occurring approximately every 3 months until the end of the safety follow-up period.. A final Follow-up Visit will be performed at the end of the safety period, 28 (± 5) days after the last open-label dose.
- ^d Informed consent must be documented before any trial-specific screening procedure is performed, and may be obtained either at the Washout or Screening Visits.
- ^e Any procedures that were not completed during washout, must be completed at the Screening Visit.
- ^f Includes respiratory rate, pulse rate, and systolic and diastolic blood pressures while the patient is in a seated position, and temperature. Abnormalities observed at baseline should be recorded on the General Medical History and Baseline Conditions eCRF. At subsequent visits, new or worsened clinically significant abnormalities should be recorded on the Adverse Event eCRF. All vital sign measurements are to be obtained prior to any blood draws scheduled at the same time.
- ^g Includes evaluation of the head, eyes, ears, nose, and throat, and the cardiovascular, dermatological, musculoskeletal, respiratory, gastrointestinal, genitourinary, and neurological systems. Abnormalities observed at baseline should be recorded on the General Medical History and Baseline Conditions eCRF. At subsequent visits, new or worsened clinically significant abnormalities should be recorded on the Adverse Event eCRF.
- ^h All ECGs are to be obtained prior to other procedures scheduled at the same time.
- ⁱ Hematology includes WBC count, RBC count, hemoglobin, hematocrit, platelet count, differential count (neutrophils, eosinophils, basophils, monocytes, lymphocytes, other cells).
- ^j Chemistry panel (serum or plasma) includes sodium, potassium, chloride, bicarbonate, glucose, BUN or urea, creatinine, total protein, albumin, phosphorus, calcium, total and direct bilirubin, alkaline phosphatase, ALT, AST, uric acid, LDH.

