4.6.5 Vital Signs

Vital signs will include measurements of respiratory rate (breaths/min), pulse rate (beats/min), and systolic and diastolic blood pressures (mmHg) while the patient is in a seated position, temperature (C) and weight (kg). Vital signs will be assigned to visit windows as per Section 4.10. Descriptive statistics will be used to summarize vital signs data at baseline and at each scheduled post-baseline visit, and for the absolute change from baseline to each scheduled post-baseline visit by treatment arm during double-blind period.

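### Weight loss is a named pirfenidone risk and the SAP treats weight as a by-visit vital sign, but the protocol schedules weight only at screening, Week 24 and about four weeks after an early stop

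*Protocol*

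**What the plan says.** Protocol 5.1.1.7 reports that in the pooled Phase 3 data "the adverse event of weight decrease was reported for a larger proportion of pirfenidone patients than placebo patients (10.1% pirfenidone vs. 5.4% placebo"), and that most affected pirfenidone patients "first did so during the initial 6 months of treatment (39/63, 61.9"%). In the same data five pirfenidone patients (0.8%), and no placebo patient, stopped treatment for this event.

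Protocol 4.5.4 defines the measurements: "Vital signs will include measurements of respiratory rate, pulse rate, and systolic and diastolic blood pressures while the patient is in a seated position", followed by temperature. Footnote f of Appendix 1 gives the same list: "Includes respiratory rate, pulse rate, and systolic and diastolic blood pressures while the patient is in a seated position, and temperature". Weight has its own row in Appendix 1, marked at screening, Week 24 and the Early Treatment Discontinuation Visit. Footnote b puts that last visit 28 (± 5) days after the last double-blind dose. The copy of the schedule in SAP Appendix 2 carries the same marks.

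SAP 4.6.5 extends the vital-signs list to include weight: "while the patient is in a seated position, temperature (C) and weight (kg"). It then says: "Descriptive statistics will be used to summarize vital signs data at baseline and at each scheduled post-baseline visit", and adds change from baseline. SAP 4.7 applies a similar analysis to vital signs in the open-label period. The section numbers it cites are those of SAP version 2.0; vital signs are now in 4.6.5. SAP 4.9 applies visit windows for Weeks 4 to 24 to vital signs. It derives an EOT visit from the early-discontinuation record for early stoppers and from the Week 24 record for completers.

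**The concern.** The two documents disagree on whether weight is a vital sign, and the disagreement falls on a risk the protocol itself singles out. Three consequences follow from the schedule.

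- A completer's net change from screening to the end of treatment is measured, but its course over Weeks 4 to 20 is not.
- A patient who stops early has no scheduled weight while taking the drug. The one later weight is taken about four weeks after the last dose.
- No weight is scheduled in the open-label year, although SAP 4.7 analyses vital signs there.

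Weight-decrease adverse events are still sought at every contact. Except at Week 24, no scheduled on-drug weighing stands behind those reports. In addition, any EOT row for weight would combine two kinds of value, end-of-treatment and off-drug, without saying so.

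**Working it through.** **Reproducing the protocol's figure.** Protocol 5.1.1.7 gives 39 of 63: 39/63 = 0.619, or 61.9%, as stated.

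**Counting scheduled weights.** The marks below are from Appendix 1. The open-label count takes six monthly visits plus about two quarterly ones.

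| Visits | Vital signs marked | Weight marked |
|---|---|---|
| Weeks 4, 8, 12, 16, 20, 24 | 6 of 6 | 1 of 6 (Week 24) |
| Early Treatment Discontinuation | yes | yes, 28 ± 5 days off drug |
| Week 28 follow-up | yes | no |
| Open-label visits (6 + about 2) | about 8 | 0 |
| Final safety visit | no | no |

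Of the six post-baseline double-blind visits, 5/6 = 83% have vital signs but no scheduled weight. Across both treatment periods, weight is scheduled at 1 of about 6 + 8 = 14 visits. There is no Day 1 weight, so under SAP 4.2.2 the screening value serves as baseline.

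**Timing of the early-stop weight.** The permitted range is 28 − 5 = 23 to 28 + 5 = 33 days after the last dose, which is 11 days. SAP 4.2.4 ends the on-treatment window for safety at the last positive dose plus 28 days. Days 29 to 33, or 5 of the 11, fall outside it. A weight taken on schedule may therefore count as on-treatment or not, depending on the day of the visit.

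**The derived visit.** Under SAP 4.9 the by-visit rows keep early stoppers apart. Their data go to a separate early-discontinuation visit, and the Week 24 window covers only patients who did not stop early. The EOT visit does not keep them apart: it takes Week 24 records for completers and early-discontinuation records for the others.

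**Scale, as illustration only.** 63/0.101 ≈ 624 pirfenidone patients in the pooled data; 39/624 ≈ 6.25%; 0.0625 × 125 ≈ 7.8, or about 8 patients in a 125-patient arm with a first report in the first six months. This carries IPF rates into another population, treats 24 weeks as 6 months, and is not net of placebo. Section 5.1.1.7 does not split the placebo rate by time, so a net figure for 24 weeks cannot be derived. Over the whole pooled follow-up the difference is 10.1% − 5.4% = 4.7 points, and 0.047 × 125 ≈ 5.9 patients. Treatment stops for weight decrease, at 0.8%, would be 0.008 × 125 = 1 patient.

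**The case against.** The strongest reply is that the SAP never promises a weight at every visit. SAP section 4 presents by-visit timepoints only as applicable. SAP 4.6.4 uses much the same wording for laboratory values, although hematology is scheduled after baseline only at Weeks 12 and 24 and at early discontinuation. On that reading the windows sort whatever was collected, and the weight table has a Week 24 row and a separate early-discontinuation row. This largely stands. A reader might infer six promised weights with five missing, but the text does not compel that. It does not remove the difference between the two definitions of vital signs, or the absence of any open-label weight for SAP 4.7 to analyse.

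The second reply is that the risk is described as an adverse event and is captured as one. Body weight is not among the safety endpoints in Protocol section 2. Adverse events are sought at each contact (5.3.1), and later visits include symptom-directed examination (4.5.3). SAP 4.6.2 tabulates weight loss and plans Kaplan-Meier onset curves for weight decreased. This also stands: it would be wrong to say that weight loss goes undetected. What is missing is scheduled measurement behind those reports.

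The third reply is that few patients drive the early-stop problem. About 1 in 125 would stop for weight decrease at the pooled rate. However, the lack of an on-drug weight applies to everyone who stops early, whatever the reason.

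**Conclusion.** The mismatch is real, and correcting it is a cheap improvement. Weight is scheduled at 1 of 6 post-baseline double-blind visits, at no on-drug visit for an early stopper, and at 0 of about 8 open-label visits. Any EOT weight row would mix end-of-treatment and off-drug values, some from outside the SAP's own safety window. These statements rest only on the schedule and the SAP definitions. They concern scheduled weights; unscheduled weighing remains possible.

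Three stronger inferences are not supported.

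- A reader might conclude that the weight table will understate the drug effect. That requires lost weight to return within about four weeks of stopping, and the documents say nothing about this, so the direction of any bias is open.
- A reader might assume that about half the open-label patients are first exposed there. Entry is optional and depends on the investigator's judgment (Protocol 4.3.4), so the split is unknown.
- A reader might see the same gap in the ECG row, which ends at Week 28. Protocol 5.1.1.8 says what to do when a prolonged QTcF is found but sets no ECG frequency, and 4.5.9 allows unscheduled ECGs. There is no contradiction there.

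**What to change.** Reconcile Protocol 4.5.4, Appendix 1 footnote f and the Weight row with SAP 4.6.5, 4.7 and 4.9.

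The preferred route is to record weight at the visits where vital signs are already taken. This would give on-drug weights before an early stop and throughout the open-label year. The estimated cost is about a minute per visit and one eCRF field. It helps only for data still to be collected: SAP 4.5.8 places the primary analysis in March 2019, before SAP version 3.0.

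Otherwise, amend the SAP text alone: restrict the weight summary to Week 24, report early-discontinuation weights separately and label them off-drug, leave them out of the EOT row, and state in 4.7 that no open-label weight is scheduled. This costs a few lines and can still be done after collection, but it recovers none of the missing on-drug weights.

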4.5.5 FVC

FVC is defined as the maximal volume of gas that can be exhaled following full inhalation by exhaling as forcefully and rapidly as possible. FVC has been an established measure of pulmonary function in patients with IPF for many decades ([du Bois et al. 2011](#)). Longitudinal changes in serial measures of lung volume are a widely accepted reflection of disease progression in patients with IPF and a commonly used primary endpoint in therapeutic studies.

If a patient is routinely treated with a short-acting bronchodilator (for example albuterol, salbutamol), the bronchodilator should be taken approximately 30 minutes prior to the on-site spirometry.

4.5.6 Handheld Spirometry

Patients will perform a single spirometry reading at approximately the same time each day. For this purpose, trial participants will be provided with a portable handheld Micro spirometer (██████████, England). The Micro spirometer measures FEV₁ and FVC by means of a turbine volume transducer and provides a digital read out registered in liters at body temperature and pressure saturated with water vapor (BTPS). Each spirometer will be factory calibrated. Patients will be given 60 minutes dedicated instruction on how to undertake spirometry at the Screening Visit. Patients will be asked to use the device during the screening period and will be subsequently retrained at the Baseline Visit. Additional refresher training will be provided after 1 month.

As the primary endpoint of this trial is to determine the rate of decline in FVC measured by daily handheld spirometer, further support to effectively use this device will be provided to the patients. The Sponsor will select a healthcare company that will be responsible for providing home nursing services for the participating sites. The vendor is responsible for ensuring that all home nursing professionals are licensed, qualified, and in good standing, as per applicable regulations, and that appropriate background checks have been performed.

Sites will communicate directly with the vendor in their country when patients have entered the trial. The trained nursing professional will conduct the visit at the patient's home or at another suitable location in order to provide handling evaluations and quality assurance for the daily spirometer assessments. The expected number of home visits is stated in the Schedule of Assessments ([Appendix 1](#)).

4.5.7 Other Trial Assessments

Further information on the other assessments (e.g., FVC, DLco, 6MWD, UCSD-SOBQ, Leicester Cough Questionnaire, cough visual analog scale, and SGRQ) that will be conducted as part of this trial can be found in [Appendix 2](#) and the Study Manual.

